## II. Research Plan and Design

Study Objectives:

**Aim 1. Compare the effects of acute, moderate intensity and acute, higher intensity exercise on cerebral glucose metabolism in nondemented (ND) elderly and AD subjects.** ND (n=30) and AD (n=30) subjects will undergo a single bout of moderate intensity (45-55% HRR) or higher intensity (65-75% HRR) exercise to assess the effect of exercise intensity on acute change in brain glucose metabolism (rest to exercise). *We hypothesize that both moderate and high intensity exercise will elicit a drop in global brain glucose metabolism compared to quiet rest, but that the effect will be greater with higher intensity vs. moderate intensity exercise, and greater in ND subjects than in AD subjects.*

**Aim 2. Characterize the effect of both exercise intensities on acute biomarker response and cognition (memory and executive function) in ND and AD subjects.** The acute biomarker response to exercise and the effect on cognition has not been examined in aged or AD cohorts. *We hypothesize that acute higher intensity exercise will elicit a greater blood lactate response (lactate area under the curve; AUC) compared to acute moderate intensity exercise, and that this response will be greater in ND than in AD subjects. We further hypothesize that lactate AUC will track negatively with change in cerebral glucose metabolism and cognitive performance.* Although we will focus on lactate, we will also quantify additional exercise-related biomarkers.

### A. Study Type and Design:

This is a cross-sectional, observational study to determine the effect of acute exercise on cerebral glucose metabolism in cognitively healthy elderly (n=30) and Probable AD (n=30). There will be 4 study visits. Individuals will be recruited from the KU Alzheimer's Disease Center (KU ADC) Clinical Cohort and Eligibility Database. The study visits are explained below, and a timeline for the FDG-PET scan visits is given in Figure 2.

Figure 2A. Resting Visit Timeline

[figure not shown]
[figure not shown]

Figure 2B. Exercise Visit Timeline

uptake, the subject will sit quietly. Background factors (lighting, noise, etc.) will be identical between V2 and V3, with the only difference being the acute exercise bout (Fig 2, A-B). We will adhere to strict timing regarding blood draws, tracer injection, and scan time. Following the scan, a short battery of executive function tests (see detailed methods) will be administered (Table 2). \*V2 and V3 will be counterbalanced.

**Visit 2/3 (~90 mins):** V3 will consist of an FDG-PET scan in early morning, after an overnight (8hr) fast, following exercise. The timing for blood draws and PET scan will match V2. *For both visits we will inject the radiotracer at the timepoint that corresponds to completion of the 5 min warm-up.* In pilot work, we showed that blood lactate levels are elevated at this time using this exact exercise protocol (Fig 3). Following the scan, a short battery of executive function tests (see detailed methods) will be administered. \*V2 and V3 will be counterbalanced.

**Visit 4. (~30 mins):** We will obtain a structural MRI, which will enhance the analysis of the PET images.

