**B. Subject Criteria (See Vulnerable Populations appendix, if applicable):**

1. Inclusion criteria:
  - Age 60 and older
  - Stable medication doses (>1month)
  - Post-menopausal
  - Diagnosis of either Nondemented (CDR 0) or Probable AD (CDR 0.5 or 1 only)
2. Exclusion criteria:
  - Inability to provide consent
  - Diagnosis of insulin-dependent (Type 1) Diabetes Mellitus
  - Recent ischemic heart disease (<2 years)
  - Diagnosis of an clinically significant chronic disease including CVD, other metabolic diseases (e.g., thyroid), cancer, HIV, or acquired immunodeficiency syndrome
  - Excluded from or unable to complete an MRI scan
  - Any Neurological disorders that have the potential to impair cognition or brain metabolism (e.g., Parkinson's disease, stroke defined as a clinical episode with neuroimaging evidence in an appropriate area to explain the symptoms).
  - Clinically significant depressive symptoms that may impair cognition, abnormalities in B12, RPR, or thyroid function that may impair cognition, use of psychoactive and investigational medications, and significant visual or auditory impairment
3. Withdrawal/Termination criteria: If the participant has a serious AE during the maximal cardiorespiratory fitness test (Visit 1) we will not have the participant return for the rest of the study. Participants are allowed to participate in other observational studies during their enrollment period but not interventional trials.

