**FDG-PET imaging:** FDG PET images will be obtained at a satellite location of the University of Kansas Hospital, the KU Cancer Center – Overland Park (KUCC-OP). The scanner is accredited by the American College of Radiology (ACR), and our physicists perform annual required testing by scanning an Esser PET phantom with 18F to assess SUV range, contrast resolution, spatial resolution, and uniformity. In addition to the ACR annual testing, the nuclear medicine department routinely performs quality control procedures on a daily, weekly, and quarterly basis. Frames are reconstructed to a single PET image in native space. Adverse events will be continuously monitored during the imaging session. The radiation dose from the two FDG PET scans will not exceed 2100 mrem. While this exceeds the amount obtained through normal background exposure, it is considered by Radiation Safety to be well below the risk levels acceptable in research and medical practice. PET images will be analyzed using custom software written for Statistical Parametric Mapping (SPM12). Pre- and post-intervention P images will be co-registered. A priori regions of interest masks from the Automated Anatomic Labeling series will be inverse warped to match native space images. The PET images will be standardized to the uptake value of the cerebellum and standardized uptake value ratios (SUVR) will be calculated from native-space ROIs as determined by MRI. Regional SUVR will be compared using paired t-tests or linear mixed models as appropriate.

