monitored during the warm up. Four minutes after the warmup begins (1 min prior to FDG injection), Draw 2 will be taken. Immediately following the 5 min warm up, FDG will be injected through the IV catheter that was placed prior to exercise. Following injection, participants will maintain cycling at either 45-55% or 65-75% of their HRR for 15 min. We will use an electronically-braked cycle ergometer (Lode, Groningen, Netherlands) to precisely control HR and workload. Rating of perceived exertion (RPE) will be collected every 2 minutes to assess effort. Participants will maintain a consistent pedaling rate (60-70 rpm) as this may affect physiological variables. [111] Immediately following the 15 min exercise at the target intensity, Draw 3 will be taken. At this time, the participant will begin a cool down period that lasts 5 min. Blood pressure will be monitored during the cooldown. The participant will dismount the bicycle and move to the scanner table. Draw 4 will be taken at 30 minutes before the scan. After the scan is complete a blood draw will be taken at minute 45 and a short cognitive performance test (NIH Toolbox Cognition Battery) will be performed. The final blood draw will be taken after the scan is complete, at minute 75. We will provide up to 120mL of water as needed to account for any dehydration that may affect blood volume during exercise. The amount of water consumed by each participant during exercise will be noted by the study coordinator.

Cognitive performance analyses (Visits 2 and 3): Most work assessing acute cognitive change following exercise has focused on executive function testing. We will administer a short battery of cognitive tests using the NIH Toolbox Cognition Battery on an iPad 5 minutes following the end of the FDG-PET scan at minute 50. These will assess executive function, attention, processing speed and episodic memory, given data linking these domains with exercise and physical activity.[1, 112] Different versions of these tests will be used between the resting and exercise visits where available.

MRI Scan (Visit 4): Structural MRI will use a Siemens 3.0 Tesla Skyra MRI scanner. We will obtain high resolution T1 weighted (MPRAGE) images following the ADNI2 standard. High-res T1 weighted anatomic images provide gross anatomy with high gray-white matter contrast (MP-RAGE; 1x1x1mm voxels; TR=2300, TE=2.98, TI=900, FOV, 1mm thickness, flip angle 9°). Neuroimages will be processed via Freesurfer. [81]

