#### **G. Location where study will be performed:**

**Performance sites:** Visit 1: KU Medical Center Clinical Research Center (CRC) Clinical and Translational Science Unit (CTSU). Visits 2 and 3: KU Cancer Center Overland Park (KUCC-OP). Visit 4: KU Medical Center, Hoglund Brain Imaging Center (HBIC). Study records will be kept at the KU CRC.

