### **G. Payment, including a prorated plan for payment:**

Subjects will receive a one-time compensation of \$200 for participating in this study. They will be given a ClinCard which works like a debit card. At Visit 3, payment will be added to the card by computer. The money will be available within 1 business day. Subjects can use the ClinCard at an ATM or at a store. They will be given one card during the study. The KUMC Research Institute will be given their name, address, social security number, and title of this study to allow them to set you up in the ClinCard system. Study payments are taxable income. A form 1099 will be sent to the subject and the Internal Revenue Service if your payments are \$600 or more in a calendar year. The subjects' personal information will be kept on a secure computer. It will be removed from the computer after the study is over and the money on the card has been used. The information will not be shared with other businesses. It will be kept confidential.

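### The only structural MRI follows both FDG-PET scans and the sole payment, so a participant who cannot complete it (an exclusion criterion) is identified only after full exposure

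*Combined protocol and SAP*

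**What the plan says.** Four parts of the combined protocol and SAP bear on this point.

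- **Eligibility (Section II.B, exclusion criteria).** One criterion reads "Excluded from or unable to complete an MRI scan". It covers people barred from MRI and people who cannot get through the scan.
- **Visit order (Sections II.A, II.E and II.G).** The rest and exercise FDG-PET scans are at Visits 2 and 3, in counterbalanced order. The only study MRI comes after them: "MRI Scan (Visit 4): Structural MRI will use a Siemens 3.0 Tesla Skyra MRI scanner".
- **Use of the MRI.** Section II.A describes it in one sentence: "We will obtain a structural MRI, which will enhance the analysis of the PET images". The FDG-PET paragraph of Section II.E goes further. It first says "A priori regions of interest masks from the Automated Anatomic Labeling series will be inverse warped to match native space images", and then that "standardized uptake value ratios (SUVR) will be calculated from native-space ROIs as determined by MRI". The same paragraph bounds the exposure: "The radiation dose from the two FDG PET scans will not exceed 2100 mrem".
- **Payment (Section III.G).** There is a single $200 payment: "At Visit 3, payment will be added to the card by computer".

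The withdrawal criteria in Section II.B deal with a serious adverse event at the fitness test. The text reviewed has no replacement rule, analysis-set rule or PET-only method for a participant without an MRI.

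**The concern.** A contraindication to MRI can be picked up from history. Inability to complete the scan, for example from claustrophobia, is confirmed only in the MRI scanner. Under the planned order that happens after the maximal fitness test, allocation to an intensity arm, both tracer injections and twelve blood draws (six at each of two visits). The second half of the exclusion criterion therefore cannot be checked by the study's own scan until everything it should protect has been done.

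Two things are at stake. A participant may receive up to 2100 mrem and then have no SUVR by the one method the plan describes. And because the failure surfaces at the last visit, the person cannot be replaced before exposure. Paying the whole sum at Visit 3 also means that nothing in the payment plan supports attendance at Visit 4.

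**Working it through.** **Order of events**

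1. Visit 1: diagnostic assessment and maximal fitness test (Section II.E).
2. Visits 2 and 3: one FDG-PET scan each. The exercise scan is done at the randomised intensity, so the arm must be set before that visit.
3. Visit 3: the only payment (Section III.G).
4. Visit 4: the MRI that Section II.E uses to determine the regions and Section II.B makes a condition of eligibility.

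A failure at step 4 is seen after steps 1 to 3 are complete.

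**Reproducing the plan's power**

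Inputs from Section V.A, sample size justification: 15 per intensity arm within a diagnosis group; effect size d = 1.25 with stated power 91%; d = 1.00 with stated power 75%; 10% attrition; 66 recruited. The significance level is not stated, so I assume two-sided 0.05.

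The plan calls the test a two-sample paired t test, but its figures match an independent two-sample t test on n per arm, with df = 2n − 2 and noncentrality d × √(n/2). For n = 15 and d = 1.25 the noncentrality is 1.25 × √7.5 = 3.42 on 28 df, giving 91.0%. At d = 1.00 the result is 75.3%. Both agree with the plan.

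**Losing participants at Visit 4**

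The same formula with fewer evaluable participants per arm:

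| n per arm | d = 1.25 | d = 1.00 |
|---|---|---|
| 15 | 91.0% | 75.3% |
| 14 | 88.9% | 72.1% |
| 13 | 86.4% | 68.7% |
| 12 | 83.3% | 64.9% |
| 11 | 79.6% | 60.7% |

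**Relation to the attrition allowance**

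- Recruiting 66 gives 66 / 4 = 16.5 per arm. After 10% attrition this is 16.5 × 0.90 = 14.85, with power 90.8% at d = 1.25. If MRI losses fall inside that 10%, power stays at about 91%.
- If MRI losses come on top of it, the result depends on a rate the documents do not give. Assuming 5%, 10% or 20%:
  - 14.85 × 0.95 = 14.11 per arm, power 89.2% at d = 1.25 and 72.5% at d = 1.00
  - 14.85 × 0.90 = 13.37 per arm, power 87.4% and 70.0%
  - 14.85 × 0.80 = 11.88 per arm, power 82.9% and 64.4%
- The allowance has no slack: 66 × 0.90 = 59.4 against a target of 60.

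**The case against.** The strongest reply is that a missing MRI need not cost the primary outcome. Section II.A calls the MRI an enhancement, the region masks come from an atlas, the two PET images are co-registered to each other, and Section V.B frames the primary outcome as a global signal. Nowhere do the documents say that PET without MRI is unusable. This stands in part: a reader might infer that every MRI failure removes a primary outcome, and the documents do not establish that. But the FDG-PET paragraph in Section II.E is the only description of how SUVR is obtained. There the MRI determines the regions, and no separate method is given for the global measure. PET-only processing may be possible, but the plan does not provide for it.

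Second, earlier screening may exist. History can identify contraindications, and Section III.A describes pre-screening. Section III.B marks a screening questionnaire as not applicable, but that does not show that MRI history goes untaken. The Visit 1 description in Section II.A is also absent from the text available here, so I do not claim that there is no MRI safety screen. Gross inability to lie still would also show during the PET scans. What remains is MRI-specific intolerance and non-attendance at Visit 4.

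Third, the statistical damage is limited. The attrition allowance spans all visits, Visit 4 included. A reader might also infer that three failures among AD participants would take that group below plan. With 66 recruited there are about 66 / 2 = 33 per diagnosis, and 33 − 3 = 30 is the planned number.

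Fourth, a reader might see a conflict with the intent-to-treat statement in Section V.A if failures were commoner in AD. The documents do not support this. Diagnosis is not randomised, and nothing suggests that MRI failure depends on intensity arm. A missing SUVR is a missing-data problem, and the lactate, biomarker and cognitive data for Aim 2 would still be available.

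**Conclusion.** The sequencing weakness is real. An eligibility condition that also feeds the described SUVR method is tested only after both tracer doses and after the sole payment, and no rule covers a failure.

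Its effect on power is modest: none to speak of if losses stay within the 10% allowance, and about two to three percentage points at d = 1.25 for each of the first two participants lost per arm below 15. About 11 per arm would be needed to fall just under 80%. These figures rest on the assumed two-sided 5% level. The MRI failure rates are illustrative.

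The case for change therefore rests on avoiding exposure that yields no evaluable SUVR and on finding failures while they can still be replaced. It does not rest on a threat to the trial's validity. Whether a missing MRI forfeits the primary outcome cannot be settled until Sections II.A and II.E are reconciled.

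**What to change.** - Schedule the same structural MRI after the Visit 1 fitness test and before the first FDG-PET visit. Placing it after the fitness test avoids scanning people who stop there.
- Require a usable T1 image before randomisation and before the first FDG injection, and replace those who fail at this step.
- Move the single payment to the last visit or prorate it, so that it does not precede a required procedure.
- State in Sections II.A and II.E whether the MRI is required for SUVR or only improves it.

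If the order cannot be changed, the minimum is a documented MRI safety and tolerance screen before the first FDG-PET visit, together with a prespecified PET-only method and a replacement and analysis-set rule for participants without an MRI.

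The cost is a protocol and scheduling amendment with the same scans and the same number of visits. Visits 1 and 4 are already both at KU Medical Center (Section II.G). The small downside is that some MRI slots will go to people who then do not proceed to PET.

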**B. Subject Criteria (See Vulnerable Populations appendix, if applicable):**

1. Inclusion criteria:
  - Age 60 and older
  - Stable medication doses (>1month)
  - Post-menopausal
  - Diagnosis of either Nondemented (CDR 0) or Probable AD (CDR 0.5 or 1 only)
2. Exclusion criteria:
  - Inability to provide consent
  - Diagnosis of insulin-dependent (Type 1) Diabetes Mellitus
  - Recent ischemic heart disease (<2 years)
  - Diagnosis of an clinically significant chronic disease including CVD, other metabolic diseases (e.g., thyroid), cancer, HIV, or acquired immunodeficiency syndrome
  - Excluded from or unable to complete an MRI scan
  - Any Neurological disorders that have the potential to impair cognition or brain metabolism (e.g., Parkinson's disease, stroke defined as a clinical episode with neuroimaging evidence in an appropriate area to explain the symptoms).
  - Clinically significant depressive symptoms that may impair cognition, abnormalities in B12, RPR, or thyroid function that may impair cognition, use of psychoactive and investigational medications, and significant visual or auditory impairment
3. Withdrawal/Termination criteria: If the participant has a serious AE during the maximal cardiorespiratory fitness test (Visit 1) we will not have the participant return for the rest of the study. Participants are allowed to participate in other observational studies during their enrollment period but not interventional trials.

**E. Specific methods and techniques used throughout the study**

1. Laboratory tests:

A catheter will be placed to facilitate multiple blood draws. We will draw ~10cc of blood into an EDTA vacutainer tube at 6 timepoints throughout Visit 2 and Visit 3. Lactate levels will be analyzed immediately in whole blood using a Lactate Meter (Nova Biomedical). Blood will be processed for platelet rich plasma (PRP) and platelet free plasma (PFP) and will be stored for analysis. After initial analyses, remaining PRP and PFP will be stored in a locked freezer in [name] laboratory (2nd floor Hemenway, badge access area).

2. Study Procedures:

Diagnostic assessment (Visit 1): We will leverage established KU ADC criteria for diagnosing subjects as ND or AD. A clinician evaluates all participants with the Clinical Dementia Rating (CDR) [74, 75] and a standard physical and neurological examination using UDS 3.0 Forms and Scales. The UDS 3.0 neuropsychological test battery is then administered. Due to COVID-19, we will be administering the CDR and neuropsychological testing (T-Cog) by telephone to reduce the amount of time spent in the clinic during Visit 1.

To participate in the study, participants will meet criteria for etiologic diagnosis of probable AD (any age, CDR 0.5 or 1) or normal aging (ND, 60 years and older). All participants are required to have a study partner (someone who routinely interacts with participant > 5 times a week) to be available to speak with the clinician via telephone. The study partner will be consented over the phone and will not be required to accompany the participant to any visits. Their involvement in the clinical evaluation will be explained by study staff and will be allowed to ask questions. The study partner will be sent a form from REDCap to add

digital signature. Exclusion criteria include significant neurological disease other than AD that may affect cognition (e.g., stroke, major depression, etc.) history of cancer within the last 5 yrs (except non-metastatic basal or squamous cell carcinoma), history of drug/alcohol abuse (DSM-IV criteria) within the last 2 yrs, and visual or auditory limitations that will interfere with the cognitive assessments. Any available clinical imaging data is also reviewed for abnormalities that may explain cognitive complaints (such as multiple lacunar infarcts or a single infarct  $> 1 \text{ cm}^3$ , prior hemorrhage  $> 1 \text{ cm}^3$ , or evidence of structural damage).

**Cardiorespiratory Fitness Testing (Visit 1):** Subjects will be tested for  $\text{VO}_2$  peak using a Bruce protocol on a treadmill as previously described [76]. Relative ( $\text{ml/kg}^{-1}/\text{min}^{-1}$ ) and absolute ( $\text{L/min}^{-1}$ )  $\text{VO}_2$  peak and treadmill time to exhaustion will be used as determinants of aerobic capacity. Our ADC has validated  $\text{VO}_2$  peak testing in AD patients [76, 77] and in older control adults [4] and currently uses the same assessment in 3 ongoing clinical exercise intervention trials. Subjects are attached to a 12-lead electrocardiograph and wear a non-rebreathing facemask to assess heart rate, blood pressure, and expired air (oxygen, carbon dioxide) using a Parvomedics system.  $\text{VO}_2$  peak is the highest observed value during the test[78, 79] and maximal effort is defined as meeting 3 of 4 criteria: a plateau in  $\text{O}_2$  consumption, a respiratory exchange ratio (RER)  $\geq 1.0$ , a maximal heart rate within 90% age-predicted maximum, or volitional fatigue.[80] If the medical monitor detects abnormalities during the ECG, physician's clearance will be required prior to PET scans. This form will be faxed to primary care or cardiologist with ECG and medical monitor's notes.

**FDG-PET imaging:** FDG PET images will be obtained at a satellite location of the University of Kansas Hospital, the KU Cancer Center – Overland Park (KUCC-OP). The scanner is accredited by the American College of Radiology (ACR), and our physicists perform annual required testing by scanning an Esser PET phantom with 18F to assess SUV range, contrast resolution, spatial resolution, and uniformity. In addition to the ACR annual testing, the nuclear medicine department routinely performs quality control procedures on a daily, weekly, and quarterly basis. Frames are reconstructed to a single PET image in native space. Adverse events will be continuously monitored during the imaging session. The radiation dose from the two FDG PET scans will not exceed 2100 mrem. While this exceeds the amount obtained through normal background exposure, it is considered by Radiation Safety to be well below the risk levels acceptable in research and medical practice. PET images will be analyzed using custom software written for Statistical Parametric Mapping (SPM12). Pre- and post-intervention P images will be co-registered. A priori regions of interest masks from the Automated Anatomic Labeling series will be inverse warped to match native space images. The PET images will be standardized to the uptake value of the cerebellum and standardized uptake value ratios (SUVR) will be calculated from native-space ROIs as determined by MRI. Regional SUVR will be compared using paired t-tests or linear mixed models as appropriate.

